  - Complete the AQLQ +12 (weeks 4, 8, 12, 16, 32, and 52 or early withdrawal only) (AQLQ+12 may be completed after study drug administration during the 1-hour observation period.)
  - Complete the SGRQ (weeks 32 and 52) (may be completed after study drug administration during the 1-hour observation period.)

- 
- Assess asthma exacerbations and related health care utilizations.
  - Collect blood for serum reslizumab concentration determination (PK assessment) from all patients (weeks 2, 4, 8, 12, 16, 20, 32, 48, and 52 or early withdrawal only).
  - Collect blood sample for immunogenicity (ADA) assessment (weeks 4, 16, 32, and 52 or early withdrawal only).
  - 

The following procedures/assessments will be performed during and after administration of study drug:

- Patients will be observed for 1 hour after study injection.
- Evaluation of injection site for reaction at approximately 1 hour after dosing using the injection site CRF. Clinically significant injection site reactions should be recorded as an adverse event.
- If, during post-study drug observation, the patient develops clinical symptoms, vital signs should be collected. The patient should be assessed for anaphylaxis/hypersensitivity reactions as detailed in Section 7.1.7.

Remind the patients that they will receive a post-injection symptom inquiry via the eDiary.

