To be eligible to enroll in the study, a patient will have an ACQ-6 score of at least 1.5, airway FEV₁ reversibility of at least 12% to beta-agonist administration, blood eosinophil count of at least 300/ μL , and a current fluticasone propionate dosage of at least a medium total daily ICS dose with a second asthma controller and will have met all the inclusion and none of the exclusion criteria at screening. The goal is to recruit a maximum of 30% of the patients (60 patients per treatment arm) with eosinophil levels of 300/ μL to $<400/\mu\text{L}$.

Patients who meet screening eligibility requirements will return to the research facility 3 weeks before baseline/DoR to confirm eligibility and begin the run-in period. At the start of run-in, patients will begin daily self-monitoring at home using an asthma control diary and PEF meter, while taking their usual asthma medications, in order to establish their baseline level of asthma control based on the frequency of symptoms, use of reliever SABA, nighttime awakenings due to asthma, and ambulatory lung function measurement. Improvement in asthma control during the treatment period will primarily be assessed by a reduction in the rate of clinically significant asthma exacerbations with reslizumab versus placebo over the 52-week treatment period.

Pulmonary function; AQLQ +12, ACQ, and SGRQ scores; asthma symptoms; use of reliever SABA; nighttime awakenings due to asthma; safety measures; PK; immunogenicity; and health care utilization events will be assessed periodically; final assessments will be made at the EOT visit (week 52) or at early withdrawal. Patients who withdraw from the study before completing the 52-week evaluation period will have visit 17 (week 52 or early withdrawal) procedures and assessments performed at their final visit. Patients will return 12 weeks after the EOT visit for follow-up hematology, PK, immunogenicity, and safety assessments.

The assessments and procedures performed during each study visit are detailed in [Table 1](#). If a patient elects to withdraw (or is discontinued from treatment by the Investigator), every attempt will be made to continue the assessments subsequent to their withdrawal from the study (see Section 4.4 of the study protocol for additional information).

A total of 450 patients are planned to be randomized in a 1:1 ratio (approximately 225 patients within each treatment group) to receive reslizumab 110 mg or matching placebo every 4 weeks for 52 weeks.

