4.5. Study Days and Visit Windows

Study days will be numbered relative to the first day of study drug administration. The start of treatment (day 1) is defined as the date on which a patient takes the first dose of study drug, as recorded on the study drug diary. Days will be numbered relative to study start (ie, ..., -2, -1, 1, 2, ...) with day 1 being the start of study drug and day -1 being the day before the start of study drug).

For safety-by-visit summaries, if there are multiple assessments at a post-baseline visit then the last non-missing assessment at that visit will be used for the analysis. This includes assessments at the scheduled and unscheduled visits.

‘Endpoint’ for safety analyses and summaries is the time point when the last observation was obtained during the treatment period. For patients who completed treatment in this study, the treatment period will be defined from the first dose of study drug to the end of treatment (week 52) visit. For patients who prematurely discontinue treatment, the treatment period will be defined from the first dose of study drug to the last dose of study drug + 4 weeks.

For efficacy-by-visit summaries, only the assessments at the scheduled visit will be summarized. The assessments at unscheduled visits will be listed. For the purpose of the efficacy analysis, assessments collected at an early termination visit will be considered as the next scheduled visit for that assessment if at least 3 but no more than 5 weeks elapsed since the date of the last medication intake.

Efficacy-by visit summaries will be presented on-treatment. In this context, ‘endpoint’ will be defined as the last observation obtained at a scheduled or qualified early termination visit during the treatment period. For patients who completed treatment in this study, the treatment period will be defined from the first dose of study drug to the end of treatment (week 52) visit. For patients who prematurely discontinue treatment, the treatment period will be defined from the first dose of study drug to the last dose of study drug + 4 weeks.

For selected variables, additional sensitivity analyses may be presented utilizing all data collected over the entire course of the study including data collected after withdrawal for patients who prematurely discontinue from treatment. In this context, ‘endpoint’ will be defined as the last observation obtained at any post-baseline scheduled or qualified early termination visit.

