6.3.3. Pulmonary Function Tests

6.3.3.1. Variable Definition

Pulmonary function tests will be measured using spirometry, according to ATS/ERS 2005 procedural guidelines. Pre-bronchodilator assessments (FVC, FEV₁, FEF_{25%-75%}) are measured at weeks 2, 4, 8, 12, 16, 32, and 52 and post-bronchodilator assessments (FEV₁) are measured at weeks 16, 32, and 52.

The FVC is the volume of air, in liters (L), that can be forcibly blown out after full inspiration. The FEV₁ is the volume of air (L) that can be forcibly exhaled from the lungs in the first second. The FEF_{25%-75%} is the forced expiratory flow (L/second) at 25% to 75% forced vital capacity. The percent (%) predicted FEV₁ is derived as the actual FEV₁ divided by the standard predicted FEV₁ (multiplied by 100). The National Health and Nutrition Examination Survey (NHANES) III reference equations will be used. An additional correction factor will be applied for Asian patients ([Hankinson et al 2010](#)).

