6.3.3.2. Analysis

Summary statistics of actual values and change from baseline to each scheduled visit will be provided by treatment group.

Analysis of the change from baseline to each scheduled visit will be performed using a mixed effect model for repeated measures (MMRM) including fixed effects for treatment, visit, treatment by visit interaction, age group (12 to <18 years and ≥ 18 years), blood eosinophil counts at enrollment (300 to <400/ μL and $\geq 400/\mu\text{L}$), and sex, height and baseline value as covariates, and patient as a random effect. Age and blood eosinophil categories will be based on data recorded in the clinical database. An unstructured covariance matrix will be used for the within patient correlation modeling. If the fit of the unstructured (UN) covariance matrix fails to converge, the following covariance structures will be tried in order until convergence is reached: first order autoregressive (AR[1]) and compound symmetry (CS). Based on the MMRM model, the treatment effect, the difference from placebo, and the associated 95% CI will be presented together with the corresponding p-value.

The following sample SAS[®] code pertains to the MMRM analysis.

```
proc mixed data=<<>>;
  class patient visit treatment strata1 strata2 sex;
  model change=treatment strata1 strata2 sex height baseline visit treatment*visit
    /ddfm=kr alpha=0.05;
  repeated visit /type=un subject=patient r;
  lsmeans treatment*visit / diff cl;
  ods output lsmeans=<<>>;
  ods output diffs=<<>>;
run;
```

Model results will only be reported if there are at least 15 patients contributing to the analysis in each treatment group; otherwise only the descriptive statistics will be displayed. A line graph presenting the LS mean change from baseline over time (at each visit) will be provided for pre-bronchodilator FEV₁, [REDACTED] by treatment group.

Pre-bronchodilator FEV₁ at Week 52 will additionally be examined for the selected subgroups defined in Section 3.4. The analysis of subgroups will use a MMRM model similar to the one described above. Subgroups will be presented graphically using forest plots.

The proportion of patients achieving an increase of ≥ 100 mL in FEV₁ from baseline to each scheduled visit will be summarized. A stratified (based on randomization strata) Cochran-Mantel-Haenszel (CMH) test will be used to analyze the proportion of patients achieving an increase of ≥ 100 mL in FEV₁ from baseline to Week 52.

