6.3.4. AQLQ +12

6.3.4.1. Variable Definition

The AQLQ +12 is a modified version of the standardized AQLQ which measures functional impairments experienced by adults ≥ 17 years of age. The AQLQ +12 is valid for patients aged 12-70 years.

The AQLQ +12 is a 32-item instrument administered as a self assessment at weeks 4, 8, 12, 16, 32, and 52. Patients are asked to recall their experiences during the previous 2 weeks and to score each question on a 7-point scale (7 = no impairment, 1 = severe impairment).

The 32 questions (items) in the AQLQ +12 are divided into 4 domains:

- Activity limitations: Items 1-5, 11, 19, 25, 28, 31, 32
- Symptoms: Items 6, 8, 10, 12, 14, 16, 18, 20, 22, 24, 29, 30
- Emotional function: Items 7, 13, 15, 21, 27
- Environmental stimuli: Items 9, 17, 23, 26

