6.3.6. SGRQ

6.3.6.1. Variable Definition

St. George's Respiratory Questionnaire (SGRQ) is a health status survey specific for chronic obstructive pulmonary disease and other respiratory diseases. The SGRQ consists of 2 parts: Part 1 produces a symptom score and Part 2 produces an activity and impacts score. A total score is also calculated. The SGRQ is administered as a self assessment at weeks 32 and 52.

The questions in the SGRQ are divided into 3 domains:

- Symptoms: Questions 1-8
- Activity: Questions 11, 15

- Impacts: Questions 9-10, 12-14, 16-17

The SGRQ requests a single response to each of Questions 1-10 and 17; whereas Questions 11-16 each request multiple responses, resulting in a total of 50 responses across the questionnaire.

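### SAP 4.5 sets no limit on how far ahead an early-termination value may be filed, so FEV1 and AQLQ +12 values taken up to 17 weeks early can count as week 52

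*SAP*

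**What the plan says.** SAP 4.5 sets the rule for by-visit efficacy data: "assessments collected at an early termination visit will be considered as the next scheduled visit for that assessment". A single condition is attached, on timing alone; the relabelling applies "if at least 3 but no more than 5 weeks elapsed since the date of the last medication intake". SAP 4.5 also counts a qualified early-termination visit as on-treatment when it falls within the treatment period, which for early discontinuers ends at last dose plus 4 weeks. SAP 6.3 makes the on-treatment approach the main one for by-visit secondary endpoints.

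The assessment schedules differ:

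- Pre-bronchodilator spirometry values "are measured at weeks 2, 4, 8, 12, 16, 32, and 52" (SAP 6.3.3.1).
- AQLQ +12 is "administered as a self assessment at weeks 4, 8, 12, 16, 32, and 52" (SAP 6.3.4.1).
- "The SGRQ is administered as a self assessment at weeks 32 and 52" (SAP 6.3.6.1).
- ACQ-6 is completed at week 2, week 4 and every 4 weeks after that (SAP 6.3.5.1).

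The visit label then drives the model: "Analysis of the change from baseline to each scheduled visit will be performed using a mixed effect model for repeated measures" (SAP 6.3.3.2). AQLQ +12 and SGRQ use the same model without sex and height.

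The documents disagree on whether SGRQ is collected at early withdrawal. SAP 2.1 says that patients who withdraw "will have visit 17 (week 52 or early withdrawal) procedures and assessments performed at their final visit", and both schedule tables mark SGRQ in the visit-17 column, which covers early withdrawal. Protocol 3.16.3.1.2 reads "Complete the SGRQ (weeks 32 and 52" and does not mention early withdrawal, although the spirometry and AQLQ +12 items beside it do. The measures section of the protocol synopsis gives SGRQ at baseline and week 32 only.

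**The concern.** An interval of 3 to 5 weeks after the last dose suits an assessment made at every 4-weekly dosing visit, because the next scheduled visit is then close by. It does not suit FEV1, AQLQ +12 or SGRQ, whose next scheduled visit can be months away.

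For an affected patient, the value stands in for a week that was never observed, much as carrying a last value forward would. The MMRM contrast at week 52 (FEV1, AQLQ +12) or week 32 (SGRQ) is then not purely a contrast at that week, and the responder tests at those weeks use the same labels. This also sits badly with SAP 4.4, which plans to use observed data only for everything except the primary variable.

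The three changes are secondary endpoints 1, 2 and 6 in a fixed sequence. FEV1 is the first gate after the primary, so its result decides whether any later endpoint is tested.

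**Working it through.** The plan states no figure on this point, so there is none to reproduce. The check enumerates what the rule does on the nominal schedule.

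**Inputs**

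- Doses every 4 weeks, 13 in total, at weeks 0, 4, …, 48 (Protocol 5.1 and schedule table). An early discontinuer's last dose is taken to be at one of the 12 weeks L = 0, 4, …, 44.
- The visit takes place at L + 3 to L + 4 weeks. The lower limit is the SAP 4.5 condition; the upper limit is the on-treatment cut.
- The target is the next scheduled visit for that assessment.
- Weeks early = target week − actual week.
- Visit windows from SAP Table 1: ±3 days at week 2, ±7 days from week 4 to week 52.

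**Result by last dose**

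| Last dose (week) | Visit (week) | FEV1 and AQLQ +12 filed as | Weeks early | SGRQ, if collected, filed as | Weeks early |
|---|---|---|---|---|---|
| 0 | 3–4 | 4 | 0–1 | 32 | 28–29 |
| 4 | 7–8 | 8 | 0–1 | 32 | 24–25 |
| 8 | 11–12 | 12 | 0–1 | 32 | 20–21 |
| 12 | 15–16 | 16 | 0–1 | 32 | 16–17 |
| 16 | 19–20 | 32 | 12–13 | 32 | 12–13 |
| 20 | 23–24 | 32 | 8–9 | 32 | 8–9 |
| 24 | 27–28 | 32 | 4–5 | 32 | 4–5 |
| 28 | 31–32 | 32 | 0–1 | 32 | 0–1 |
| 32 | 35–36 | 52 | 16–17 | 52 | 16–17 |
| 36 | 39–40 | 52 | 12–13 | 52 | 12–13 |
| 40 | 43–44 | 52 | 8–9 | 52 | 8–9 |
| 44 | 47–48 | 52 | 4–5 | 52 | 4–5 |

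The two extremes are 52 − 35 = 17 weeks (FEV1, AQLQ +12) and 32 − 3 = 29 weeks (SGRQ).

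**Positions outside the target visit's ±7 days**

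- FEV1 and AQLQ +12: 3 filed as week 32 plus 4 filed as week 52 = 7 of 12. Only the 4 are at the tested week.
- SGRQ: 7 filed as week 32 plus 4 filed as week 52 = 11 of 12. Only the 7 are at the tested week.
- ACQ-6: 0 of 12; it is never more than 1 week early.

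**Variations.** If the week-32 dose is given 7 days early, at week 31, and the visit is at week 34, the gap is 52 − 34 = 18 weeks. In the all-data sensitivity analyses the visit may be up to 5 weeks after the last dose. Reading the next visit by calendar, a last dose at week 28 and a visit one day after week 32 gives a gap of 19.86 weeks. The 17 weeks is thus the nominal maximum for the main analysis, not an absolute one.

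**Illustration of size (assumed inputs).** Suppose a share of one arm's week-52 FEV1 records is relabelled, and each differs from that patient's own week-52 value by a fixed amount in one direction. Shift in the raw contrast = share × difference:

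- 1% × 50 mL = 0.5 mL
- 5% × 200 mL = 10 mL

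Equal shifts in both arms cancel.

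**The case against.** The wording and both maxima are hard to dispute. The case on the other side is that few patients are reached and the effect is small.

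**Reach.** To affect the main analysis a patient must leave the study, attend a withdrawal visit, attend it in the one-week band 3 to 4 weeks after the last dose, and have the last dose inside a long gap. Patients who stop drug but stay have their discontinuation visit recorded as unscheduled (Protocol 4.4.1), and SAP 4.5 only lists unscheduled efficacy values. Protocol 3.16.4 asks for final evaluations on the last dosing day or as soon as possible after it, so many visits made as instructed would fall before 3 weeks and never be relabelled. This stands. It does not empty the band: a patient who decides to leave when the next 4-weekly visit is due qualifies.

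**Counts.** Positions are not patients, and only 4 of 12 reach the week-52 tests directly. That is correct and is why the counts above are split by target week.

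**SGRQ.** The 29-week case needs SGRQ to be collected at early withdrawal, departure after one dose and a return inside the band. It is a corner case resting on inconsistent text, and carries less weight than the FEV1 and AQLQ +12 point.

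**Size.** Even the top of the illustration is one tenth of the SAP's 100 mL FEV1 responder threshold, and no changed test result is shown. True, but it bears on priority, not on whether the label is right.

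**Convention.** These are new on-treatment measurements, each used once, so the comparison with carrying forward is loose, and the fix gives them up. It also uses scheduling windows as analysis windows for these values alone. This is fair, but a measurement at week 35 is still not one at week 52, and the later visit can be left missing in the MMRM.

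**Conclusion.** The concern holds. As written, SAP 4.5 places FEV1 and AQLQ +12 values up to 17 weeks early into week 52 and, if SGRQ is collected at early withdrawal, SGRQ values up to 29 weeks early into week 32. No other provision limits the distance, and the on-treatment cut retains visits at 3 to 4 weeks.

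These figures assume the nominal dosing and visit schedule. Confidence is high for the rule and for the FEV1 and AQLQ +12 gaps, and moderate for SGRQ. The documents give no dropout rate or timing, so the number of patients cannot be derived; the 0.5 to 10 mL range is an illustration, not an estimate. The direction of bias is not known in advance. The primary endpoint is not affected, and ACQ-6 is affected by at most 1 week in the main analysis. This should be corrected because it mislabels data in gated endpoints and is cheap to put right, not because a large effect has been shown.

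**What to change.** Amend SAP 4.5 so that an early-termination efficacy assessment is assigned to a scheduled visit only if its study day falls within that visit's own window in SAP Table 1 (±3 days at week 2, ±7 days from week 4 to week 52). Otherwise list the value and treat the later visit as missing in the MMRM. On the nominal schedule this leaves every on-treatment ACQ-6 assignment unchanged.

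Reconcile the SGRQ text so that the SAP and protocol say plainly whether the questionnaire is collected at early withdrawal.

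The cost is one or two sentences of SAP wording before unblinding, with no new data. The price is a few fewer records at weeks 32 and 52.

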5. STUDY POPULATION

5.1. General

The ITT analysis set will be used for all study population summaries, unless otherwise noted. Population summaries will be presented by treatment group and overall.

5.2. Patient Disposition

Data from patients screened, patients screened but not randomized, and the reason the patients were not randomized will be summarized overall (for all screened patients). Patients randomized (ITT analysis set), patients randomized but not treated, patients randomized but not analyzed (Section 3), patients in the safety analysis set, patients in the PP analysis set, patients who completed treatment (all 52 weeks while on study treatment), patients who completed the planned treatment phase (remained active in the study for the full 52 week duration, either on- or off-treatment), and patients who completed the study will be summarized. Patients will be categorized as completed the study if they either complete the study visits up to and including follow-up (Week 64, for patients not participating in the LTE study) or up to and including end of treatment (Week 52, for patients participating in the LTE study). Data from patients who withdrew early will be summarized by reason for withdrawal, and the number of patients who discontinued treatment but continued to attend study visits will be tabulated.

KM plots will be provided for time to discontinuation from treatment to identify if there is a differential dropout pattern between the treatment groups.

5.3. Demographics and Baseline Characteristics

Baseline demographics (eg, age, sex, race, ethnicity) and patient characteristics (eg, spirometry, airway reversibility) including smoking history, medical history, phadiatop test results, and prior medications will be summarized to assess the comparability of the treatment groups. Baseline stratification factors (age and blood eosinophil counts) and patients taking the various classes of background asthma medication (defined in Section 3.4.4) will also be summarized. Baseline demographics and patient characteristics will also be summarized separately for patients who discontinue from treatment and patients who complete treatment to investigate whether patients with and without missing values may have different characteristics at baseline.

Age will be calculated based on the date of birth relative to the screening visit (date of informed consent). If regional data regulations prohibit collection of a full date of birth, then the patient's age should be recorded on the CRF, if possible. If only a year of birth has been collected (and age has not otherwise been reported) then the missing date of birth will be imputed as 30 June (30 June YYYY) in order to derive the patient's age at baseline.

5.4. Medical History

All medical history abnormalities will be coded using the Medical Dictionary for Regulatory Activities (MedDRA). The incidence of medical history abnormalities will be summarized by

system organ class (SOC) and preferred term (PT). Patients are only counted once in each SOC and once in each PT.

Asthma- and allergy-specific history will also be collected and reported. In addition, descriptive statistics will be provided for time since asthma diagnosis, time since most recent exacerbation, number of exacerbations within the last 12 months, and number of days missed school/work due to asthma in the past year.

History of nasal polyp, whether sinus surgery was performed, time since sinus surgery, whether diagnosed by CT scan, time since CT scan, and anosmia will be summarized.

5.5. Prior Medications

All prior medications will be coded using the World Health Organization dictionary of medical codes (WHO Drug). The incidence of prior medications will be summarized by therapeutic class and preferred term. Patients are only counted once in each therapeutic class and once in each preferred term. Prior medications include all medications with a start date prior to the first day of study drug.

Prior medications for asthma will be summarized separately. In addition, total ICS dose taken at baseline will be summarized. The reported ICS doses will be converted to fluticasone equivalents using the following conversion factors. ICS dose at baseline will be defined as the dose taken at the time of randomization.

Table 4: Conversion of ICS to Fluticasone-Equivalent Doses

Inhaled corticosteroid (mcg)	Conversion factor
Fluticasone	1
Fluticasone furoate	2
Mometasone	1.14
Budesonide ^a	0.625
Ciclesonide	1.56
Beclomethasone	1.25
Triamcinolone	0.25

^a Nebulized budesonide is typically recorded in mg and, if applicable, the reported dose (in mg) may need to first be converted to mcg (x1000) prior to applying the indicated conversion factor for budesonide.

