### 4.1. Patient Inclusion Criteria

Patients may be included in this study only if they meet all of the following criteria:

- a. Written informed consent is obtained. A patient 12 through <18 years of age must provide assent, and their parent(s) or legal guardian(s) must provide consent.
- b. The patient is male or female, 12 years of age and older, with a diagnosis of asthma. (Patients 12 to <18 years of age are excluded from participating in South Korea and Argentina, and patients 66 years of age and older are excluded from participating in South Korea.)
- c. The patient has had at least 2 documented asthma exacerbations requiring the use of systemic (oral, intramuscular, or iv) corticosteroids within 12 months of signing the Informed Assent Form/Informed Consent Form.
- d. The patient has an ACQ-6 score of at least 1.5 at screening (visit 1).
- e. The patient has a blood eosinophil level of at least 300/ $\mu$ L during the screening period (ie, before visit 2). (A maximum of 30% of the patients [60 patients per treatment group] with blood eosinophil levels of 300/ $\mu$ L to <400/ $\mu$ L will be enrolled. When this 30% threshold has been reached, only patients with blood eosinophil levels of  $\geq$ 400/ $\mu$ L will then be enrolled.)
- f. The patient has an FEV1 reversibility of at least 12% after administration of inhaled SABA according to standard American Thoracic Society (ATS) or European Respiratory Society (ERS) protocol. Documented historical reversibility within 12 months of signing the Informed Assent Form/Informed Consent Form is acceptable.
- g. The patient has required at least a medium total daily ICS dose based on GINA 2016 clinical comparability table ([Appendix A](#)) for at least 3 months. For ICS/LABA combination preparations, the mid-strength approved maintenance dose in the local country will meet this ICS criterion.
- h. The patient has required an additional asthma controller medication (eg, long-acting beta-2-agonist [LABA], long-acting muscarinic antagonist [LAMA], leukotriene receptor antagonist [LTRA], or theophylline preparations), besides ICS, for at least 3 months or a documented failure in the past 12 months of an additional asthma controller medication for at least 3 successive months.

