## APPENDIX A. GLOBAL INITIATIVE FOR ASTHMA ICS CLINICAL COMPARABILITY TABLE

**Table 7: Medium or Higher Daily Doses of Inhaled Corticosteroids in Patients 12 Years and Older**

Drug	Daily Dose (µg)	
	Medium	High
Beclomethasone dipropionate (CFC) a	>500	>1000
Beclomethasone dipropionate (HFA)	>200	>400
Budesonide (DPI)	>400	>800
Ciclesonide (HFA)	>160	>320
Fluticasone fuorate (DPI)	N/A	≥200
Fluticasone propionate (DPI)	>250	>500
Fluticasone propionate (HFA)	>250	>500
Mometasone furoate	>220	>440
Triamcinolone acetonide	>1000	>2000

[figure not shown]
Source: Adapted from Box 8 in GINA 2016 Update ([www.ginasthma.org](http://www.ginasthma.org)).

[figure not shown]
a Beclomethasone dipropionate CFC is included for comparison with older literature.

[figure not shown]
CFC = chlorofluorocarbon propellant; DPI = dry powder inhaler; HFA = hydrofluoroalkane propellant; N/A = not applicable.

[figure not shown]

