3.4.4. Asthma Background Medication

Patient classifications based on Global Initiative for Asthma (GINA) guidelines ([GINA 2015](#)) will be derived. Selected efficacy endpoints including CAEs and pre-bronchodilator FEV₁ will be examined for the following medication classes taken at baseline. Medications at baseline will be defined as those taken at the time of randomization.

- **GINA 4 – ICS/LABA+ (Yes, No)**
Note: “Yes” is defined as patients taking ICS (medium or high-dose); and LABA or leukotriene or xanthine as a second controller; and no OCS use
 - ICS/LABA (Yes, No)
Note: “Yes” is defined as patients taking ICS (medium or high-dose); and LABA as a second controller; and no OCS use
 - High-dose ICS/LABA (Yes, No)
Note: “Yes” is defined as patients taking ICS (high-dose); and LABA as a second controller; and no OCS use
 - Medium-dose ICS/LABA (Yes, No)
Note: “Yes” is defined as patients taking ICS (medium-dose); and LABA as a second controller; and no OCS use

- **GINA 5** – OCS (Yes, No)
Note: “Yes” is defined as patients taking OCS

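### The SAP's background-therapy subgroups leave out LAMA as a second controller, and its ICS conversion table disagrees with protocol Appendix A for fluticasone furoate and CFC beclomethasone

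*SAP*

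**What the plan says.** SAP 3.4.4 sets up background-medication subgroups for CAEs and pre-bronchodilator FEV1, citing GINA 2015. GINA 4 is Yes for medium- or high-dose ICS "and LABA or leukotriene or xanthine as a second controller; and no OCS use". Three narrower Yes/No splits follow for ICS/LABA overall, high-dose and medium-dose. GINA 5 is Yes for any patient taking OCS. The section gives no µg cut-offs for medium or high dose and refers to neither SAP Table 4 nor protocol Appendix A.

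Protocol 4.1, criterion h, gives as examples of the additional controller LABA, "long-acting muscarinic antagonist [LAMA], leukotriene receptor antagonist [LTRA], or theophylline preparations". SAP Table 2 (major protocol violations) also names LAMA as an acceptable second controller.

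On dose, SAP 5.5 says "In addition, total ICS dose taken at baseline will be summarized" and that "The reported ICS doses will be converted to fluticasone equivalents using the following conversion factors". One row of Table 4 reads "Fluticasone furoate 2". Protocol Appendix A, titled "Medium or Higher Daily Doses of Inhaled Corticosteroids in Patients 12 Years and Older", has the rows "Fluticasone fuorate (DPI) N/A ≥200" and "Fluticasone propionate (DPI) >250 >500" (µg per day, medium then high). Criterion g bases ICS eligibility on that table, in its GINA 2016 form, and also admits ICS/LABA combinations at the locally approved mid-strength maintenance dose.

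**The concern.** There are two separate defects.

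First, the GINA 4 list of second controllers is narrower than the eligibility criterion and narrower than the SAP's own Table 2. Some eligible patients fit neither GINA 4 nor GINA 5, and the GINA 4 No group pools them with patients on oral corticosteroids. A rate ratio in that No group, and the CAE interaction p-value that compares it with the Yes group, then have no clear meaning in terms of background treatment.

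Second, 3.4.4 relies on medium- and high-dose labels that it does not define, while the SAP's only numerical ICS scale (Table 4) disagrees with the protocol table for two preparations. Two programmers could reasonably give the same fluticasone furoate patient opposite dose classes. Even without that, the baseline ICS dose summary puts these preparations on a scale that does not match the eligibility table.

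**Working it through.** **Dose conversion.** Inputs: factors from SAP Table 4; high-dose cut-offs from protocol Appendix A, Table 7. Assumption: Fluticasone with factor 1 in Table 4 means propionate, whose medium band is above 250 and up to 500 µg. Check: factor × the drug's own high cut-off should be about 500.

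| Drug | Factor | High cut-off (µg) | Product |
|---|---|---|---|
| Fluticasone propionate | 1 | 500 | 500 |
| Mometasone | 1.14 | 440 | 501.6 |
| Budesonide | 0.625 | 800 | 500 |
| Ciclesonide | 1.56 | 320 | 499.2 |
| Beclomethasone HFA | 1.25 | 400 | 500 |
| Triamcinolone | 0.25 | 2000 | 500 |
| Fluticasone furoate | 2 | 200 | **400** |
| Beclomethasone CFC | 1.25 | 1000 | **1250** |

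Six rows agree with Appendix A to rounding; two do not.

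- Furoate: 200 × 2 = 400, in the propionate medium band, while Appendix A calls 200 µg high and gives furoate no medium class. With factor 2 the dose would have to exceed 500/2 = 250 µg to pass 500. For the two tables to agree at 200 µg the factor would have to exceed 500/200 = 2.5. At exactly 2.5 the product is 500, which is still not above 500.
- CFC beclomethasone: Appendix A implies 500/1000 = 0.5. Table 4 has one beclomethasone factor and does not separate the propellants.

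**Class logic.** Applying the 3.4.4 definitions to a patient on medium- or high-dose ICS:

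| Additional treatment | GINA 4 | GINA 5 |
|---|---|---|
| LABA, leukotriene or xanthine; no OCS | Yes | No |
| LABA + LAMA; no OCS | Yes | No |
| LAMA only; no OCS | **No** | **No** |
| LAMA, or any of the above, with OCS | No | Yes |

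So the GINA 4 No group contains all OCS users plus the LAMA-only patients without OCS. Patients who qualified under criterion h through documented past failure of a controller, and who now take neither a second controller nor OCS, fall into the same gap.

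**Where the variables are used.** They appear in the baseline summaries (SAP 5.3, 5.5), the CAE subgroup analysis with an interaction p-value and forest plot (SAP 6.2.5), and the FEV1 subgroup analysis by MMRM with a forest plot, for which no interaction test is stated (SAP 6.3.3.2). The primary model (SAP 6.2.2) contains treatment, age category, eosinophil category and number of exacerbations in the previous year. It has no ICS-dose or GINA term.

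**The case against.** The strongest reply is that the two SAP sections are not connected. Table 4 serves one descriptive item and 3.4.4 never cites it. A reader might infer that fluticasone furoate users will be moved from high to medium dose; the documents do not say so. That happens only if an analyst applies Table 4 totals and propionate cut-offs to 3.4.4, and then only for furoate doses up to 250 µg. This part of the reply stands. What remains is that the medium/high rule is unspecified.

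A reader might also infer that the SAP contradicts a protocol classification. The protocol text available defines no GINA 4 or GINA 5 class. The LAMA omission is an inconsistency with criterion h and with SAP Table 2. Nor are LAMA-only patients dropped: each class is a separate Yes/No split and they are analysed as No. Mixed No groups are inherent in one-versus-rest subgroups, and OCS users are examined separately under GINA 5. All of that is fair, but the SAP gives no reason for leaving out a controller that it accepts elsewhere.

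It is tempting to say that the furoate dose is understated. That presumes Appendix A is right and Table 4 wrong. Appendix A gives furoate a class boundary and no potency ratio, and nothing in the documents settles which should change. For CFC beclomethasone, Appendix A says the row is there for comparison with older literature, so few or no patients may be affected. Finally, 3.4.4 cites GINA 2015 and eligibility cites GINA 2016. The protocol's change log shows a furoate row added with the 2016 update; the documents do not show any wider difference.

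**Conclusion.** The point holds as a minor one. By the text of 3.4.4, eligible patients on ICS plus LAMA alone without OCS are No for both GINA classes and are grouped with OCS users. By arithmetic, Table 4 and Appendix A disagree for fluticasone furoate (400 against a high class that starts above 500) and for CFC beclomethasone (1250 against 500). Any effect of the second defect on dose class depends on Table 4 being used for 3.4.4, which the SAP does not state.

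The reach is confined to baseline summaries and the background-therapy subgroups for CAEs and FEV1. These lie outside the fixed testing sequence (SAP 4.3 and 6.3.1), and the primary analysis is untouched. The documents give no counts of LAMA-only, furoate or CFC beclomethasone patients, so no number of affected patients can be stated. The calculation assumes that Table 4's Fluticasone row means propionate.

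**What to change.** 1. In SAP 3.4.4, add LAMA to the GINA 4 second-controller list, or state why it is excluded. Say also where patients with no current second controller and no OCS belong.
2. State that medium or high ICS dose is assigned by the protocol's own eligibility rule, that is Appendix A together with the criterion g provision for ICS/LABA combinations, and not by Table 4 equivalents. Appendix A alone is not enough, because the combination provision admits patients whom its drug-by-drug cut-offs might not place.
3. Reconcile the Table 4 furoate and beclomethasone entries with Appendix A, and separate HFA from CFC if both can occur in the data.

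A single mutually exclusive background-therapy variable is optional. It would make the groups easier to read, but small cells could fall below the SAP's minimum of 15 patients per treatment group for reporting the FEV1 model.

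The cost of items 1 to 3 is SAP wording and derivation code, with no change to data collection or to the primary analysis.
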